2.2 Secondary Objective(s)

- 2.2.1 To describe the QOL in patients with advanced ovarian cancer treated with NAC followed by CRS with HIPEC at 3 and 6 months post-treatment.
- 2.2.2 To describe neurotoxicity in patients with advanced ovarian cancer treated with NAC followed by CRS with HIPEC.
- 2.2.3 To describe abdominal discomfort in patients with advanced ovarian cancer treated with NAC followed by CRS with HIPEC.
- 2.2.4 To describe toxicities in patients with advanced ovarian cancer treated with NAC followed by CRS with HIPEC.
- 2.2.5 To describe the response rate in patients with advanced ovarian cancer treated with NAC followed by CRS with HIPEC.
- 2.2.6 To estimate progression-free survival (PFS) in patients with advanced ovarian cancer treated with NAC followed by CRS with HIPEC.

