6.4 Duration of Therapy

Therapy (HIPEC) will be administered for 90 minutes with carboplatin 800 mg/m² during the surgery as described in Section 6.2.1.2 of this protocol.

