13.0 Statistical Considerations

13.1 Analysis of Primary Objective

This is a descriptive study. The primary objective is to compare the QOL in patients with advanced ovarian cancer treated with SOC NAC followed by CRS with HIPEC vs. QOL in patients treated with IV chemotherapy at 6 weeks post-treatment presented in Armstrong et al. (2006). Only the patients treated with SOC NAC followed by CRS with HIPEC will be recruited in this study. The summary data of QOL for patients treated with IV chemotherapy collected in Armstrong et al. (2006) will be directly used. The same as Armstrong et al., QOL will be measured using the Fact-O questionnaire and treatment as a continuous outcome. The distribution of QOL at 6 weeks post-treatment will be examined. The descriptive statistics such as mean, standard deviation, median and interquartile range will be calculated. One sample t-test will be used to compare the mean QOL in the study sample to the mean QOL based on Armstrong et al.

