13.2 Analysis of Secondary Objective

13.2.1 To describe QOL in patients with advanced ovarian cancer treated with SOC NAC followed by CRS with HIPEC as determined by the FACT-O questionnaire at 3 and 6 months post-treatment, the distribution of QOL at 3 and 6 months post-treatment will be examined. The descriptive statistics of QOL at 3 and 6 months post-treatment will be presented. In addition, the longitudinal data of QOL over time will be displayed graphically with individual trajectories.

13.2.2. To describe neurotoxicity at the end of study, the descriptive statistics will be presented. Since neurotoxicity is a 4-item measure from FACT/GOG-NTX4, counts and percentages will be calculated. Mean and standard deviation will be also calculated.

A Phase II Trial Evaluating Quality of Life After HIPEC in Patients with Stage IIIC and IV Ovarian, Fallopian Tube or Primary Peritoneal Carcinoma
Wake Forest Baptist Comprehensive Cancer Center (WFBCCC)
CCCWFU 83216

13.2.3. To describe abdominal discomfort at the end of study, the descriptive statistics will be presented. The abdominal discomfort is a 4-item score from FACT-GOG/AD. Counts and percentages will be calculated. Mean and standard deviation will be also calculated.

13.2.4. The toxicities will be measured by the number and severity of adverse events defined by CTCAE v5.0. Counts and percentages will be calculated for each adverse event. Mean, standard deviation, median, and interquartile range will be calculated for number of adverse events.

13.2.5. The response rate using RECIST criteria at each time point will be estimated. Counts and percentages will be calculated.

13.2.6. This secondary objective is to estimate progression free survival using survival analysis. Survival will be measured up to the time until progression, date of last contact, or death, whichever comes first. Kaplan-Meier survival curves will be used to estimate the survival probabilities. The survival probabilities for the whole sample and for the stratified groups (weekly or 3-weekly) will be calculated. The log-rank test will be used to compare the two stratified groups.

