13.3 Power and Sample Size

The power calculation is performed to test the primary objective. It is calculated to compare the mean QOL between the study patients and the mean QOL from Armstrong et al. (2006). Based on Armstrong et al., the standard deviation of QOL at 6 weeks post treatment is 19.2. Fifty patients will be recruited. The dropout rate is anticipated to be very small, around 1 to 2% at 6 weeks post treatment. Assuming 80% power, a two-sided test and a significance level of 20%, the minimal detectable difference of QOL between the study sample and Armstrong et al. is 5.9. If assuming a higher dropout rate, say 10% at 6 weeks post treatment, the minimal detectable difference for QOL is 6.1. Based on Armstrong et al., the mean difference of QOL between the two standard treatments (IV vs. intraperitoneal) is 5.2. We assume that the mean difference between HIPEC and IV can be larger. However, we are also aware that we may not have enough power to detect the difference. This study is for the descriptive purpose. The data collected in this study can be very useful for future research.

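### Section 13.2.6 plans a log-rank test between weekly and 3-weekly groups that the readable text does not define, and gives PFS no start date and a last-contact end point although tumour assessment is scheduled only at 3, 6 and 12 months

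*Combined protocol and SAP*

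**What the plan says.** **Objective.** Section 2.2.6 reads "To estimate progression-free survival (PFS) in patients with advanced ovarian cancer treated with NAC followed by CRS with HIPEC". It lists no subgroup comparison.

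**Analysis.** Section 13.2.6 plans Kaplan-Meier curves and states: "The survival probabilities for the whole sample and for the stratified groups (weekly or 3-weekly) will be calculated". It continues: "The log-rank test will be used to compare the two stratified groups". It gives no significance level, group sizes or expected number of events. The time variable is set by "Survival will be measured up to the time until progression, date of last contact, or death, whichever comes first". No start date is given.

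**Design.** Section 13.1 says "Only the patients treated with SOC NAC followed by CRS with HIPEC will be recruited in this study". Section 6.4 describes the study therapy as a single procedure: "Therapy (HIPEC) will be administered for 90 minutes".

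**Tumour assessment.** Sections 6.1 and 6.5 schedule it at 3, 6 and 12 months. Section 6.5 also asks for an evaluation of disease extent when a patient leaves the trial without documented progression. Appendix F records whether a scan was done (yes, no or N/A) and, separately, whether there is progression. It calls for the measurement form (Appendix G) at first progression.

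**Other definitions.** The only time-to-event definition in section 8 is in 8.6. It is for disease-free survival, runs from completion of treatment and does not name death. Section 5.2.5 names RECIST v1.1 for response rates. Section 8.1 applies the 2000 RECIST publication to response and progression, with at most 10 target lesions. Appendix G has 5 target-lesion rows.

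**The concern.** A test between two groups needs groups that an analyst can reconstruct, a question that the test answers, and some basis for reading a difference as an effect of the grouping. The readable text supplies none of these. A small p-value could be reported as evidence about a chemotherapy schedule, and a large one as evidence of no difference. Neither reading would be justified.

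The PFS definition leaves two choices open. Without a start date, two analysts can draw different curves from the same data. With follow-up running to last contact, a patient who was seen or telephoned but not assessed for tumour stays in the risk set as progression-free. That can only push the estimate upward. The RECIST differences leave it unclear which criteria and how many lesions determine a response.

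**Working it through.** **1. Are the groups defined anywhere?**

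| Place | What it gives |
|---|---|
| 3.1.3 and Appendix A | Number of neoadjuvant cycles (3 to 6), no interval |
| 6.2 and 6.4 | One HIPEC procedure, no chemotherapy interval |
| 7.0 | Weekly evaluation of patients whose treatment is delayed; not a stratum |
| Appendices A, B, D to G and K; questionnaires H to J | No field for weekly or 3-weekly |
| Appendix K | Cycle start and end dates, but adverse-event monitoring starts at surgery |
| Schema; Tables A and B; No HIPEC Follow-Up form | Named or cited but not shown |

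The label could mean neoadjuvant schedule. It could also mean postoperative schedule: the heading of 6.2.1 mentions subsequent chemotherapy, and 7.1.3.1 refers to later cycles. On neither reading is allocation shown to be random. Section 12.0 mentions randomising participants, but this has no counterpart elsewhere and does not fit the single cohort of 13.1.

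**2. The plan's own sample-size figure.** Section 13.3 says "The power calculation is performed to test the primary objective". Its inputs are SD 19.2, 80% power and two-sided 20%. With the normal approximation, (1.282 + 0.842) × 19.2/√49 = 5.82 (noncentral t: 5.87), and with n = 45 it is 6.08 (t: 6.13). The stated 5.9 and 6.1 reproduce. No figure is given for PFS.

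For context only, the detectable hazard ratio at two-sided 5% and 80% power is exp[(1.960 + 0.842)/√(d·p·(1−p))], with d events and a proportion p in one group. With all 50 patients having events and an even split, it is exp(2.802/√12.5) = 2.21. With 25 events (assumed) it is exp(2.802/2.5) = 3.07.

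**3. Size of the censoring effect at month 12.** Suppose R of 50 patients reach the month-12 visit progression-free with no earlier censoring. Of these, u are contacted but not assessed, and a fraction f of the R − u scanned patients progress.

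- Follow-up to last contact: S₁₂ = (R/50)·[1 − f(R − u)/R].
- Censoring at last assessment: S₁₂ = (R/50)·(1 − f).
- Difference: (R/50)·(f·u/R) = u·f/50, whatever R is.

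Check with R = 36, u = 3 and 11 of 33 progressing: 36/50 × 25/36 = 0.500, against 36/50 × 22/33 = 0.480. The difference is 2.0 points, and 3 × (1/3)/50 = 0.020.

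The documents give neither u nor f. As a stand-in for u, the dropout rates in 13.3 were borrowed: 2% of 50 is 1 patient, and 10% ("If assuming a higher dropout rate, say 10% at 6 weeks post treatment") is 5. Those rates refer to week 6 and to dropout, so this is only a scale.

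| Overstatement (points) | u = 1 | u = 2 | u = 5 |
|---|---|---|---|
| f = 20% | 0.4 | 0.8 | 2.0 |
| f = 1/3 | 0.7 | 1.3 | 3.3 |
| f = 50% | 1.0 | 2.0 | 5.0 |

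For comparison, the 95% CI half-width at 50% PFS with 50 patients is 1.96 × √(0.5 × 0.5/50) = 0.139, or about 14 points.

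A simulation with heavier assumptions agrees in direction. It used exponential PFS, contact to 18 months, deaths ignored, and 20% to 40% of month-12 scans missed. Last-contact follow-up gave 0.54 to 0.58 against a true 0.50 (median 12 months) and 0.73 to 0.76 against 0.71 (median 24 months). Censoring at the last scan recovered the true value to within about 0.003. With no missed scan there was no bias at month 12.

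**4. RECIST.** Version 1.1 is attached to response rates only, and the 2000 criteria to response and progression. The text allows up to 10 target lesions, while the form has 5 rows. Because Appendix F uses that form to document first progression, the lesion-count mismatch reaches PFS through the form.

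**The case against.** Several counter-arguments have force.

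- **A definition may exist out of view.** The Schema and some cited tables and forms are not shown. One cannot say that the groups are undefined everywhere, only that the readable text and the forms shown do not define them. Even with a definition, the lack of an objective and of any shown randomisation would remain.
- **Confounding.** A reader might infer that the comparison is certainly confounded by choice of neoadjuvant schedule. The documents do not say which schedule is meant. If it is postoperative, the grouping is a post-baseline factor, which is a different problem. What stands is that no reading supports an effect of schedule.
- **Power.** A reader might fault the test for low power. Section 13.1 calls the study descriptive, 13.3 concedes limited power even for the primary comparison, and secondary tests in 50 patients are rarely powered. The hazard ratios above are context, and the point does not rest on them.
- **Censoring is partly handled.** The evaluation at discontinuation in 6.5 narrows the gap between last contact and last assessment. Physical examination is scheduled at every follow-up visit, and 8.5 accepts superficial palpable lesions as measurable, so an unscanned visit is not always an unassessed one. This reduces the effect, but 13.2.6 still does not tie follow-up to an assessment.
- **RECIST and PFS.** A reader might infer that two RECIST versions govern PFS. They do not: v1.1 is cited only for response rates, and surgery aims to remove all gross tumour, which limits the influence of a target-lesion cap on progression. The inconsistency is mainly a response-rate matter.
- **Section 8.6.** Disease-free survival is neither an objective nor an outcome, so it is probably a leftover. If treatment means the HIPEC procedure, its origin is the day of surgery.

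**Conclusion.** The point holds in limited form. The planned log-rank test has no group definition in the readable text, no data source on any form shown and no objective. Its p-value would not be interpretable as a schedule effect on either reading of the label. PFS lacks a start date, and its last-contact end point can bias the estimate upward.

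That bias is modest: about 0.4 to 5 points at month 12 for 1 to 5 unassessed patients and 20% to 50% progression among those scanned. Both ranges are assumptions. The bias is nil at month 12 if all scans are done and larger if scans are often missed. It would be wrong to conclude that the PFS estimate is necessarily biased, or that the primary quality-of-life analysis is touched: PFS is secondary. The RECIST and 8.6 discrepancies are plain inconsistencies in the text, and their numerical effect cannot be derived from the documents.

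**What to change.** - **13.2.6, groups.** Remove the log-rank test. Keep the schedule groups only if they are defined and recorded on a form suited to when the schedule occurs: at registration if neoadjuvant, in follow-up if postoperative. Then show them descriptively, without a test.
- **13.2.6, PFS.** Define PFS from the date of surgery/HIPEC to first progression or death from any cause. Censor at the last tumour assessment (scan or protocol-accepted examination) without progression. Report Kaplan-Meier estimates with 95% CIs.
- **8.6.** Replace the disease-free survival definition with this one, or delete it.
- **5.2.5, 8.1 and Appendix G.** Use one RECIST version and one target-lesion maximum.

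Dating scans at their nominal month is an optional choice and not part of this change.

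**Cost.** The changes are wording edits with no new visits or scans, and the surgery date is already on Appendix D. Measurements for patients already enrolled may need re-reading under the chosen RECIST version. If the groups are kept, schedule may have to be abstracted retrospectively. The PFS estimate may be slightly less favourable. The text should be settled before PFS is analysed.

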13.3 Power and Sample Size

The power calculation is performed to test the primary objective. It is calculated to compare the mean QOL between the study patients and the mean QOL from Armstrong et al. (2006). Based on Armstrong et al., the standard deviation of QOL at 6 weeks post treatment is 19.2. Fifty patients will be recruited. The dropout rate is anticipated to be very small, around 1 to 2% at 6 weeks post treatment. Assuming 80% power, a two-sided test and a significance level of 20%, the minimal detectable difference of QOL between the study sample and Armstrong et al. is 5.9. If assuming a higher dropout rate, say 10% at 6 weeks post treatment, the minimal detectable difference for QOL is 6.1. Based on Armstrong et al., the mean difference of QOL between the two standard treatments (IV vs. intraperitoneal) is 5.2. We assume that the mean difference between HIPEC and IV can be larger. However, we are also aware that we may not have enough power to detect the difference. This study is for the descriptive purpose. The data collected in this study can be very useful for future research.

13.4 Estimated Accrual Rate

Accrual is expected to be 40 patients in 18 months. Targeted accrual should be met within 1 ½ years. Under the current amendment (Protocol Version Date: 03/14/2023), an additional 10 patients will be recruited at an accrual rate of 1 patient per month.

13.5 Estimated Study Length

The total study length is approximately 3 years. The estimated study length for the current amendment (Protocol Version Date: 03/14/2023) is approximately 2 years.

13.6 Interim Analysis Plan

Interim reviews will be performed at 6 weeks, 3 and 6 months post-treatment to assess accrual, retention, the incidence of AEs and SAEs.

A Phase II Trial Evaluating Quality of Life After HIPEC in Patients with Stage IIIC and IV Ovarian, Fallopian Tube or Primary Peritoneal Carcinoma
Wake Forest Baptist Comprehensive Cancer Center (WFBCCC)
CCCWFU 83216

References

1. SEER Cancer Statistics Factsheets: Ovary Cancer. <http://seer.cancer.gov/statfacts/html/ovary.html>.
10. Raftery AT. Regeneration of peritoneum: a fibrinolytic study. *J Anat*. 1979;129(Pt 3):659-664.

Appendix A – Subject Eligibility Checklist

IRB Protocol No. 00044434	CCCWFU Protocol No. 83216					
Study Title: A Phase II Trial Evaluating Quality of Life After HIPEC in Patients with Stage IIIC and IV Ovarian, Fallopian Tube or Primary Peritoneal Carcinoma						
Principal Investigator: [name].						
Inclusion Criteria (as outlined in study protocol)	Criteria is met	Criteria is NOT met	Source Used to Confirm *			
Patients must have histologically or cytologically confirmed non-mucinous, epithelial stage 3 or 4 carcinoma of the ovary, fallopian tube or peritoneum.						
Patients must not have received treatment for another malignancy within 3 years of enrollment						
Patients must have received at least 3 but not more than 6 cycles of carboplatin-doublet based IV chemotherapy AND achieved at least stable disease (radiographically confirmed) at the conclusion of this therapy.						
Age \geq 18 years						
ECOG performance status \leq 2.						
Patients must have adequate organ and marrow function as defined below (within 30 days of registration): -absolute neutrophil count \geq 1,500/mcL -platelets \geq 75,000/mcL -total bilirubin \leq 1.5 mg/dL - creatinine clearance \geq 50 mL/min -AST(SGOT)/ALT(SGPT) \leq 3 X institutional upper limit of normal -alkaline phosphatase \leq 3 X institutional upper limit of normal						
The effects of HIPEC on the developing human fetus are unknown. For this reason, and because carboplatin doublet therapy consists of pregnancy category D agents, women of child-bearing potential must agree to use adequate contraception (hormonal or barrier method of birth control; abstinence) prior to study entry and for the duration of study participation. Should a woman become pregnant or suspect she is pregnant while participating in this study, she should inform her treating physician immediately.						

A Phase II Trial Evaluating Quality of Life After HIPEC in Patients with Stage IIIC and IV Ovarian, Fallopian Tube or Primary Peritoneal Carcinoma
 Wake Forest Baptist Comprehensive Cancer Center (WFBCCC)
 CCCWFU 83216

Ability to understand and the willingness to sign an IRB-approved informed consent document			
Exclusion Criteria (as outlined in study protocol)	Criteria NOT present	Criteria is present	Source Used to Confirm *
Patients may not be receiving any other investigational agents.			
Patients with extra-abdominal metastatic disease			
History of allergic reactions attributed to compounds of similar chemical or biologic composition to carboplatin doublet agents.			
Uncontrolled intercurrent illness including, but not limited to ongoing or active infection, symptomatic congestive heart failure, unstable angina pectoris, cardiac arrhythmia, or psychiatric illness/social situations that would limit compliance with study requirements			
Pregnant women are excluded from this study because carboplatin doublet therapy consists of pregnancy category D agents with the potential for teratogenic or abortifacient effects. Because there is an unknown but potential risk for adverse events in nursing infants secondary to treatment of the mother with carboplatin doublet therapy, breastfeeding should be discontinued			
Men are excluded from participation due to the site-specific nature of the disease being studied			

This subject is eligible / ineligible for participation in this study.

WISER Assigned PID: _____

Signature of research professional confirming eligibility: _____ Date: ____/____/____

Signature of Treating Physician: _____ Date: ____/____/____

Signature of Principal Investigator**: _____ Date: ____/____/____

* Examples of source documents include clinic note, pathology report, laboratory results, etc. When listing the source, specifically state which document in the medical record was used to assess eligibility. Also include the date on the document. Example: "Pathology report, 01/01/14" or "Clinic note, 01/01/14"

**Principal Investigator signature can be obtained following registration if needed

A Phase II Trial Evaluating Quality of Life After HIPEC in Patients with Stage IIIC and IV Ovarian, Fallopian
Tube or Primary Peritoneal Carcinoma
Wake Forest Baptist Comprehensive Cancer Center (WFBCCC)
CCCWFU 83216

Appendix B – Protocol Registration Form

DEMOGRAPHICS

Patient: Last Name: _____ First Name: _____

MRN: _____ DOB (mm/dd/yy): ____ / ____ / ____

Ethnicity (choose one): Hispanic

Non-Hispanic

Race (choose all that apply): WHITE BLACK ASIAN

PACIFIC ISLANDER NATIVE AMERICAN

Height: _____.____ inches Weight: _____.____ lbs. (actual)

Surface Area: _____.____ m²

Primary Diagnosis: _____

Date of Diagnosis: ____ / ____ / ____

PROTOCOL INFORMATION

Date of Registration: _____ / _____ / _____

MD Name (last): _____

Date protocol treatment started: _____ / _____ / _____

Informed written consent: YES NO

(consent must be signed prior to registration)

Date Consent Signed: _____ / _____ / _____

PID # (to be assigned by WISER): _____

Protocol Registrar can be contacted by calling [contact] between 8:30 AM and 4:00 PM, Monday – Friday.

Completed Eligibility Checklist and Protocol Registration Form must be hand delivered, faxed or e-mailed to the registrar at

Appendix C – Mandatory STRC SAE Reporting Guidelines

Safety and Toxicity Review Committee (STRC) Serious Adverse Event (SAE) Notification SOP	Date: 07/10/2019
---	------------------

Mandatory STRC SAE Reporting Requirements in WISER

This document describes reporting requirements of adverse events from **WFBCCC Investigator Initiated interventional trials to the Safety and Toxicity Review Committee (STRC)**. A trial is considered a **WFBCCC Investigator Initiated interventional trial** if the following criteria are met:

- 1) The Principal Investigator (PI) of the trial is a member of a department at the Wake Forest University Baptist Medical Center.
- 2) WFBCCC is considered as the primary contributor to the design, implementation and/or monitoring of the trial.
- 3) The trial is designated as “Interventional” using the Clinical Research Categories definitions provided by the NCI in the Data Table 4 documentation.
<https://cancercenters.cancer.gov/GrantsFunding/DataGuide#dt4>

There are two distinct types of WFBCCC Investigator Initiated interventional trials based on where patient enrollment occurs. These include:

- 1) Local WFBCCC Investigator Initiated interventional trials defined as trials where **all patients are enrolled from one of the WFBCCC sites**. These include the main outpatient Cancer Center clinics (located in Winston-Salem) as well as WFBCCC affiliate sites located in Bermuda Run (Davie Medical Center), Clemmons, Lexington, High Point, or Wilkesboro.
- 2) Multi-Center WFBCCC Investigator Initiated interventional trials defined as trials where patients are enrolled from other sites in addition to WFBCCC sites.

There are three types of trials that are included in this category:

- a. Trials sponsored by the NCI Community Oncology Research Program (NCORP) that are conducted at multiple sites where the PI is a member of a department at the Wake Forest University Baptist Medical Center.
- b. Trials sponsored by Industry that are conducted at multiple sites and the PI is a member of a department at the Wake Forest University Baptist Medical Center.
- c. Trials sponsored by WFBCCC that are conducted at multiple sites and the PI is a member of a department at the Wake Forest University Baptist Medical Center.

All Adverse Events (AEs) and Serious Adverse Events (SAEs) that occur on any patients enrolled on WFBCCC Investigator Initiated Interventional trials must be entered into the WISER system. The only exception to this requirement is for patients enrolled on NCORP trials at non- WFBCCC sites. AEs and SAEs for NCORP patients enrolled at WFBCCC sites must be entered into the WISER system. Once these AEs and SAEs are entered in WISER, certain actions must be taken regarding the reporting of specific Adverse Events to the STRC.

All Adverse Events that occur during protocol intervention (defined below) and are coded as either 1) **unexpected grade 4**, 2) **unplanned inpatient hospitalization > 24 hours (regardless of grade)**, or **grade 5 (death)** must be reported to the STRC using the SAE console in WISER.

A research nurse or clinical research coordinator when made aware that an adverse event meets one of the above criteria has occurred on a WFBCCC Investigator Initiated interventional trial, is responsible for informing a clinical member of the STRC by phone (or in-person) about the adverse event. The

nurse/coordinator should contact the treating physician prior to calling the STRC clinical member to obtain all details of the SAE, as well as all associated toxicities to be recorded along with the SAE. In addition, this nurse or coordinator is responsible for entering the adverse event information into the SAE console in WISER. Once the adverse event has been entered into the SAE console an email informing the entire STRC committee will be generated.

THESE REPORTING REQUIREMENTS APPLY TO any staff member on the study team for a WFBCCC Institutional Interventional trial. Ultimately, the protocol PI has the primary responsibility for AE identification, documentation, grading and assignment of attribution to the investigational agent/intervention. However, when an AE event as described above is observed, it is the responsibility of the person who observed the event to be sure that it is reported to the STRC.

What is considered during protocol intervention?

During protocol intervention is considered to be the time period while a patient is on study treatment or during the time period within 30 days of last study treatment (even if patient begins a new (non-study) treatment during the 30 days). This window of 30 days should be the standard window to be used in all protocols unless a specific scientific rationale is presented to suggest that a shorter window can be used to identify events. If it is a trial sponsored by Industry and the sponsor requires a longer window for monitoring of SAEs, then the longer window of time specified by the sponsor should be followed.

What is considered as an Unexpected Grade 4 event?

Any grade 4 event that was not specifically listed as an expected adverse event in the protocol should be considered as unexpected. A grade 4 adverse event can be considered to be unexpected if it is an event that would not be expected based on the treatment being received or if it is unexpected based on the health of the patient. In either case, if there is any uncertainty about whether a grade 4 adverse event is expected or unexpected it should be reported to STRC.

STRC notification responsibilities of the person (e.g., nurse) handling the reporting/documenting of the SAE in WISER:

1. Make a phone call (or speak in person) to the appropriate clinical member of the STRC as listed below (page if necessary)
2. Enter a new SAE into the SAE module that is located in the Subject>> CRA Console in WISER **WITHIN 24 HOURS** of first knowledge of the event. Information can be entered and saved, but the STRC members will not be notified until a date is entered into the STRC Notification Date Field. This will ensure that all persons that need to be made aware of the event (i.e., study team members and STRC members) will be notified; remember to file a copy of the confirmation.
3. Document that the appropriate person(s) on the STRC has been contacted. Indicate the name of the STRC clinician that was contacted in the Event Narrative field in the SAE console of the particular subject.
4. Document whether or not the protocol should be suspended based on the discussion with the STRC clinician. This is the major function of the email notification. Enter whether the protocol should be suspended in the Event Narrative Field.
5. Follow up/update the clinical member(s) of STRC regarding any new developments or information obtained during the course of the SAE investigation and reporting process.

Elements needed to complete the SAE form in the Subject Console in WISER (see Screen Shot 3):

1. Event Date
2. Reported Date
3. Reported by
4. If Grade 5, enter Death Date

5. If Grade 5, enter Death occurred: within 30 days
6. Event Narrative: Brief description (include brief clinical history relevant to this event, including therapies believed related to event). Begin narrative with the STRC clinician who was notified and Date/Time notified. In addition, state attribution by STRC clinician as either "Unrelated", "Unlikely", "Possibly", "Probably", or "Definitely". Always include the following here:
 - i. STRC clinician name and comments
 - ii. Date of last dose before the event
 - iii. Is suspension of the protocol needed? Y/N
7. Treating Physician comments
8. PI comments, if available
9. Protocol Attribution after discussion with STRC clinician
10. Outcome (Fatal/Died, Intervention for AE Continues, Migrated AE, Not Recovered/Not Resolved, Recovered/Resolved with Sequelae, Recovered/Resolved without Sequelae, Recovering and Resolving)
11. Consent form Change Required? Y/N
12. SAE Classification *This is required in order for the email notification to be sent*
13. Adverse Event Details – Enter all details for each AE associated with the SAE.
 - a. Course start date
 - b. Category
 - c. AE Detail
 - d. Comments
 - e. Grade/Severity
 - f. Unexpected Y/N
 - g. DLT Y/N
 - h. Attributions
 - i. Action
 - j. Therapy
 - k. Click ADD to attach the AE Detail to the SAE.
14. Enter Date Notified STRC -- *This is required for the email notification to be sent*
15. Click Submit. The auto-generated notification email will disseminate within 5 minutes. If you do not receive an email within 5 minutes, check that you have entered the "Date Notified STRC" and the "SAE Classification". If these have been entered and the email still has not been received, take a screen shot of the SAE in WISER and immediately email it out to all of the STRC members listed in this SOP. In the subject line, indicate that this is a manual transmission of the SAE in lieu of the auto-generated email. It is required that a notification goes to the STRC members immediately so that their assessment can be obtained within the 24 hour time frame requirement. Contact the Cancer Center Programmer/Analyst to alert that there is an issue with the auto-generated email.

The Clinical Members of STRC to Notify by Phone or Page:

Definition of Unavailable:

As a general guideline if the first clinician that is contacted does not respond to the phone call or page within 30 minutes, then initiate contact with a different STRC clinician. Allow up to 30 minutes for the new STRC clinician to respond to a phone call or page before contacting another member. These times (30 minutes) are a general guideline. Best judgment as a clinical research professional should be used giving considerations of the time of day, severity of the SAE, and other circumstances as to when it is appropriate to contact backup clinicians. If the event occurs near the end of day, then leave messages (voice or email) as appropriate and proceed with submitting the STRC notification form. It is important to take reasonable steps and to document that some type of contact has been initiated to one or more of the clinical members of STRC.

STRC CLINICAN RESPONSIBILITY:

It is the responsibility of the STRC clinician to review all reported events, evaluate the events as they are reported; and communicate a response to the Investigator, event reporter and the members of STRC. The review will include but not be limited to the information reported; there may be times when additional information is needed in order for an assessment to be made and further communication directly with the investigator may be warranted. STRC reserves the right to disagree with the Investigator's assessment. If STRC does not agree with the Investigator, STRC reserves the right to suspend the trial pending further investigation. If there is any immediate danger or harm that could be present for a future patient based on the information provided in the STRC report then an immediate suspension of enrollment should be considered.

AMENDMENTS TO PREVIOUS REPORTS

If all pertinent information is unavailable with the initial submission, once the additional information is available **do not submit a new report**. Rather, go to the original email that was sent to the STRC and using that email "reply to all". Entitle this new email "**Amendment** for (list date of event and patient ID)" this will avoid duplications of the same event. List the additional information being reported. This information needs to be entered into WISER as well. To do this, go to the Subject console and click SAEs on the left column. Click on the appropriate SAE number that needs updating. Then click update. This will allow additional information to be added

Acronyms

AE – Adverse Event

STRC-Safety and Toxicity Review Committee

SAE-Serious Adverse Event

WFBCCC – Wake Forest Baptist Comprehensive Cancer Center

NCI-National Cancer Institute

WISER –Wake Integrated Solution for Enterprise Research

Screen Shots:

The following screen shots come from the SAE Console within the Subject Console in WISER.

Screen Shot 1:

This screenshot shows the SAE Console within the Subject Console in WISER. The left sidebar menu is visible with the 'SAEs' option selected. The main content area displays subject demographic information: Last name [REDACTED], First name [REDACTED], Middle name [REDACTED], Expired date [REDACTED], Ethnicity Non-Hispanic, and Last date known alive [REDACTED]. Below this is a 'Subject Comments' section and an 'Additional Subject Identifiers' table. The table includes columns for Identifier Type, Identifier, and Identifier Owner, with a note 'No information entered'. The 'Contact Information' section follows, with tables for Primary Contact and Emergency Contacts, both showing 'No information entered'. The bottom of the screen includes a copyright notice: Copyright 2002-2018 Forte Research Systems. All rights reserved.

Screen Shot 2:

This screenshot shows the SAE Console within the Subject Console in WISER. The left sidebar menu is visible with the 'SAEs' option selected. The main content area displays a list of records. At the top, it shows Protocol No.: CCCWFUB215, MRN: [REDACTED], Protocol Status: OPEN TO ACCRUAL, Subject Name: [REDACTED], and Subject Status: ON TREATMENT, Sequence No.: [REDACTED]. A search bar 'Switch Subject' is present. The list area shows 'No Records Found'. A 'New' button is located in the bottom right corner of the list area, circled in red. The bottom of the screen includes a copyright notice: Copyright 2002-2018 Forte Research Systems. All rights reserved.

Screen Shot 3:

Protocol No. CCCWF088215
Subject Name [REDACTED]
Subject Status: OPEN TO ACCRUAL
Subject Status: OPEN STUDY
Sequence No. [REDACTED]

Subject ID: [REDACTED]

Event Details: Event Start Date: 10/22/2018, Event End Date: 10/22/2019, Date Occurred: Within 30 days, Action: [REDACTED]

Training Details: Notified Sponsor: [REDACTED] (highlighted in red), Team Reviewed: [REDACTED] (highlighted in red)

Screen Shot 4:

Protocol No. CCCWF088215
Subject Name [REDACTED]
Subject Status: OPEN TO ACCRUAL
Subject Status: OPEN STUDY
Sequence No. [REDACTED]

Subject ID: [REDACTED]

Event Details: Event Start Date: 10/22/2018, Event End Date: 10/22/2019, Date Occurred: Within 30 days, Action: [REDACTED]

Training Details: Notified Sponsor: [REDACTED] (highlighted in red), Team Reviewed: [REDACTED] (highlighted in red)

